# 10.1.2 Informed Consent and Subject Privacy

The purpose, procedures, risks, benefits, and alternatives to study participation will be discussed with each potential subject. The subject must also give Authorization for Use and Release of Health and Research Study Information, including digital images, and other written documentation in accordance with the relevant country and local privacy requirements (where applicable) prior to any study-related procedures or change in treatment.

The PI or his/her authorized designee conducts the informed consent (IC) discussion and will document in the subject's medical records the acquisition of IC and the subject's agreement or refusal to notify his/her primary care physician about the study. The IC shall include all aspects of the study that are relevant to the subject's decision to participate throughout the study. The IC process is to avoid any coercion or undue influence on, or inducement of, the subject to participate. The subject is to personally sign and date the IC. The TI will retain the original copy of the signed form, and the subject will receive a copy. Upon signing the ICF, the subject is considered enrolled in the study and receives a subject number that will be used on all documentation for the subject throughout the study. Subject numbers will be assigned in ascending order, and numbers will not be omitted or reused. The subject number is coupled with the site identification number for unique identification of each subject. The TI is to ensure important new information is provided to new or existing subjects throughout the study. For studies involving emergency treatments, when prior IC of the subject is not possible because of the subject's medical condition, the IC of the subject's legally authorized representative shall be requested. Arrangements shall be made to inform the subject or legally authorized representative, as soon as possible, about the subject's inclusion in the study and about all aspects of the study. The subject shall be asked to provide IC for continued participation as soon as his/her medical condition allows.

# **10.1.3 Method for Assignment to Treatment Groups**

At the time of randomization (ie, at or within 30 days after screening/signing of the ICF), eligible subjects will be assigned to 1 of 2 treatment groups (treatment or control) in a 3:1 ratio to receive VOLUX XC or go to the control group based on a central randomization schedule. An automated IWRS will be used to manage the randomization and treatment assignment based on a randomization scheme prepared by Allergan. Sites will dispense treatment according to the IWRS instructions provided by the system.

# 10.2 Compliance with Protocol

The PI is responsible for compliance with the protocol at the investigational site. A representative of Allergan will make frequent contact with the PI and his/her research staff and will conduct regular monitoring visits at the site to review subject and device accountability records for compliance with the protocol. Any protocol deviations will be discussed with the PI upon identification. The use of the data collected for the subject will be discussed to determine if the data are to be included in the analysis. All protocol deviations will be reported to the IRB according to the IRB reporting requirements.

### 10.3 Pregnancy

If a female becomes pregnant during the study, the PI/TI (or designee) will notify Allergan immediately after the pregnancy is confirmed. The PI/TI (or designee) shall (1) instruct the subject to notify her physician of the presence of the investigational device and (2) follow the pregnancy to term or termination. Best practices are to be followed in order to ensure the welfare of the subject and the fetus. The Allergan Medical Safety Physician will contact the PI/TI to obtain information about the pregnancy outcome. The subject will continue to be followed, and the pregnancy will be documented as a protocol deviation.

Pregnancy by itself will not be considered an AE or SAE. Hospitalization for a normal delivery or elective abortion of a normal fetus does not constitute an SAE. However, the occurrence of an adverse pregnancy outcome for the mother or child may constitute an AE or SAE, and these are to be reported as described in Sections 11.3 and 11.4.

# **10.4** Study Termination

If conditions arise during the study that indicate that the study or an investigational site needs to be terminated, Allergan, PI, Monitor, IRB, and/or regulatory agencies will discuss the

situation and take appropriate action after consultation. Conditions that may warrant termination of the study or site include, but are not limited to:

- The discovery of an unexpected, serious, or unacceptable risk to subjects enrolled in the study
- The decision on the part of Allergan to suspend or discontinue testing, evaluation, or development of the study device
- Failure of the PI to comply with pertinent national or state regulations, IRB-imposed conditions, or protocol requirements
- PI submission of knowingly false information to Allergan, Monitor, IRB, or any regulatory agency
- If a vascular embolic AE leading to skin necrosis, vision loss, or stroke occurs, all treatments at the investigational site will be suspended while the circumstances of the event are investigated. If the event is confirmed to be a vascular embolic event and related to VOLUX XC treatment, Allergan will suspend any further enrollment and treatments at the investigational site while performing a root cause analysis. If the AE is a result of deviation from the injection procedure, the investigator may be retrained and allowed to continue enrolling subjects. If the event is not a result of deviation from the injection procedure, all enrollment and treatments at all investigational sites will be halted until the event can be characterized, and a strategy to avoid further AEs can be developed.

Per International Organization for Standardization (ISO) 14155, if a study is prematurely terminated or suspended due to safety issues, Allergan shall inform all investigators and the regulatory authorities of the termination or suspension and the reason(s) for the termination or suspension. The IRB is also to be informed promptly and provided the reason(s) for the termination or suspension by Allergan or by the investigator, as specified by the applicable regulatory requirements. If a premature termination or suspension occurs, Allergan shall remain responsible for providing resources to fulfill the protocol obligations and existing agreements for follow-up of subjects enrolled in the study, and each investigator or authorized designee shall promptly inform enrolled subjects, if applicable.

#### 11. Adverse Events

Throughout the course of the study, all AEs will be monitored and reported on an AE eCRF, including seriousness, severity, action taken and relationship to study treatment. If AEs occur, the first concern will be the safety of the study participants.

Although the risk of developing a serious complication is small, the TI and the research staff will monitor each subject closely, and, if a complication occurs, they will use their medical judgment to do whatever is necessary to treat the subject. If subjects have any ongoing treatment-related SAEs at the time of the final visit, they must continue to be followed up until resolution of these events or the subject condition is considered stable by the TI. After the final visit, the subject will resume receiving the standard medical care according to the

Typical or expected AEs or risks include bruising, swelling, redness, tenderness, and/or itching at the treatment site. Additional information about the possible side effects is available in the IDFU for VOLUX XC.

#### 11.1 Definitions

standard care of the clinic.

JUVÉDERM VOLUX™ XC

### 11.1.1 Adverse Event

An AE is defined in accordance with ISO 14155 as "any untoward medical occurrence, unintended disease or injury, or untoward clinical signs (including abnormal laboratory findings) in subjects, users, or other persons, whether or not related to the investigational medical device." This definition includes events related to the investigational medical device or comparator and events related to the procedures involved except for events in users or other persons, which only include events related to investigational medical devices.

Disease signs and symptoms that existed prior to the study treatment are not considered AEs unless the condition recurs after the subject has recovered from the pre-existing condition or the condition worsens in intensity or frequency during the study.

AEs will be monitored throughout the study beginning with signing of the ICF. At each post-baseline visit, the TI (or designee) will begin querying for AEs by asking each subject a general, non-directed question such as "Have you had any changes to your condition since your last visit?" In addition, the TI will ask the subject a general, non-directed question about vision symptoms, "Since your last visit, have you experienced any changes in or around either eye? For example, loss of vision, blurriness, double vision, pain in or around the eye, blindness, blind spots, problems moving your eyes, skin changing color around the eyes, or crusty or scabby skin around the eyes." Subjects will be informed that they are to call the site if they experience any symptoms consistent with these events. Previous AEs and changes in therapy/concomitant medications are to be updated. Directed questioning and examination will then be done as appropriate and may include an in person visit at the investigation site

and/or referral to a retinal specialist. Any subject with any vision loss will be referred immediately to a retinal specialist for examination. All reportable AEs and clinically significant abnormal laboratory findings will be documented on the appropriate eCRF.

The following is a list of known potential AEs, including those related to visual symptoms:

- Redness, bruising, swelling, swelling, tenderness to touch, firmness or a rash, which may be associated with itching, pain on pressure, after the injection.
- Pain at injection site
- Bruising
- Nodules or "lumpiness" at the injection site
- Discoloration of the injection site
- Tenderness or pain in the jaw when chewing, which can usually be treated with over-the-counter painkiller and generally resolves within a few days
- Numbness, problems with chewing and mild speech related difficulties which typically resolve without treatment within a few days
- Rare cases of allergy, severe sensitivity, localized inflammation and abscesses
- Very occasionally, delayed side effects can occur many months after the treatment. These delayed side effects may include: lumps, bumps, nodules, cysts, swelling, pain, bruising, skin tightness, and product dislocation.
- In rare circumstances, facial fillers have been injected into blood vessels causing blockage and embolization which can result in skin necrosis, ulceration, or vision changes. Risks to vision include complete blindness, partial blindness, blurred vision, double vision, loss of peripheral vision, loss of a portion of the visual field or anterior segment ischemia (characterized by decreased vision and pain). These effects can be temporary or permanent but are rare.
- In rare circumstances, facial fillers have been associated with granulomas, which are small inflammatory nodules under the skin.
- In rare circumstances, stroke

Unforeseeable risks or results are also a possibility. The risk of developing a serious complication is small. If a complication occurs, subjects will be advised to contact the TI who will use his/her medical judgment to do whatever is necessary to treat the subject. In the event of vision loss, the subject must also be referred to a retinal specialist for evaluation and appropriate care.

#### 11.1.2 Adverse Event of Special Interest

An AE of special interest (AESI) is defined as any vision-related AE. See Section 11.3 for procedures of reporting an AESI.

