# 11.2 Timelines for Reporting

The TI (or designee) is to adhere to the following schedule in reporting different types of AEs.

Adverse Event Type	Reporting to Allergan	Start of Collection	End of Collection
AEs, ADEs	Record on AE eCRF upon awareness for review by the clinical monitor	Signing ICF	Last subject visit
AESI	Record on AE eCRF and fax/e-mail to Allergan within 24 hours of awareness	Signing ICF	Last subject visit
SAEs, SADEs	Record on SAE Form and fax/e-mail Allergan within 24 hours of awareness	Signing ICF	Last subject visit

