5.6.3. Adverse Events

An AE will be considered a TEAE if the AE began or worsened (increased in severity or became serious) on or after the date (and time, if known) of the initial treatment for the treatment group and on or after the date of randomization for the control group. An AE will be considered a TESAE if it is a TEAE that additionally meets any SAE criterion.

A TEAE will be considered a treatment-related AE if the TEAE is deemed related to the procedure or the study device by the TI.

CONFIDENTIAL

JUVÉDERM VOLUX™ XC

Statistical Analysis Plan V25L-002

An AESI is defined as any vision-related TEAE. The incidence of AESI will be summarized separately for CP, TP, and RP in descending order of PT, if the total number of participants with AESI is at least 5.

Overall summary will be provided on a per-participant level for TEAEs, treatment-related TEAEs, TESAEs, deaths, and TEAEs leading to study intervention discontinuation. If more than one event is coded to the same PT for the same participant, the participant will be counted only once for that PT using the greatest severity for the summarizations by severity and most related occurrence for the summarizations by relationship to study intervention. If the severity of a TEAE is missing, the maximum severity will be assigned to the event for the summarization by severity. The value will be displayed as missing in the data listing. If the relationship to the study intervention is missing for a TEAE, the event will be considered related to the study intervention for the summarization. The value will be displayed as missing in the data listing.

TEAEs will be summarized by treatment group for CP using the Safety population. TEAEs will also be summarized for TP and RP using the VT and VRT populations, respectively.

The number and percentage of participants with TEAEs and the events in the following AE categories will be summarized for the above populations as described in [Table 5-10](#). For participants who received maintenance treatment, their AEs reported during the three months in the initial treatment period will be summarized and presented in parallel with AEs reported during the maintenance treatment period.

Summary tables will be provided for participants with TESAEs and participants with TEAEs leading to discontinuation if these occurred in 5 or more participants. Listings of all TEAEs, AESIs, TESAEs, TEAEs leading to discontinuation, and death will be presented.

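### Embolic skin necrosis judged non-serious triggers the site-suspension rule but has no 24-hour notice to the sponsor, who must decide the later steps

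*Protocol*

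**What the plan says.** **The suspension rule (Protocol 10.4).** The first step is: "If a vascular embolic AE leading to skin necrosis, vision loss, or stroke occurs, all treatments at the investigational site will be suspended". No seriousness condition is attached. If the event is then confirmed as embolic and related to the device, "Allergan will suspend any further enrollment and treatments at the investigational site while performing a root cause analysis". If a departure from the injection procedure was not the cause, "all enrollment and treatments at all investigational sites will be halted until the event can be characterized".

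**The AESI definition (Protocol 11.1.2).** "An AE of special interest (AESI) is defined as any vision-related AE". SAP 5.6.3 repeats the restriction for treatment-emergent events: "An AESI is defined as any vision-related TEAE".

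**The reporting timelines (Protocol 11.2).** There are three lines:
- AESIs: "Record on AE eCRF and fax/e-mail to Allergan within 24 hours of awareness".
- SAEs and SADEs: "Record on SAE Form and fax/e-mail Allergan within 24 hours of awareness".
- All other AEs and ADEs: "Record on AE eCRF upon awareness for review by the clinical monitor".

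Section 11.3 repeats the 24-hour duty for AESIs and adds a sponsor notice to FDA for AESIs within 10 working days. Section 11.4 requires immediate notice of SAEs and SADEs. Section 11.1.1 lists skin necrosis after embolization among the known risks of facial fillers.

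**The concern.** The protocol names three embolic outcomes that start the suspension procedure, and the later steps of that procedure belong to the sponsor. For one of the three, vision loss, the sponsor is told within 24 hours whether or not the event is serious. For the other two, fast notice depends on the event being classed as serious. Stroke would ordinarily be so classed. Skin necrosis need not be.

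A pausing rule with a central decision maker works as intended only if each trigger reaches that decision maker promptly. Here one trigger can arrive by the same route as a routine adverse event. Until the sponsor knows of it, it cannot confirm the event, start the root-cause analysis or decide about other sites.

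**Working it through.** No sample size, power or error rate enters this point, and the plan gives no figure to reproduce. The check follows each trigger in Protocol 10.4 through the definitions in 11.1.2 and 11.1.3 to the reporting routes in 11.2 to 11.4.

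| Trigger in 10.4 | AESI under 11.1.2? | SAE under 11.1.3? | Notice to the sponsor |
|---|---|---|---|
| Vision loss | Yes | Not needed for notice | 24 hours, serious or not |
| Stroke | No | Ordinarily yes | 24 hours, by the SAE/SADE route |
| Skin necrosis meeting a seriousness criterion | No | Yes | 24 hours, by the SAE/SADE route |
| Skin necrosis judged non-serious | No | No | eCRF entry for monitor review; no active notice, no review deadline |

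Step 1. Section 10.4 applies to all four rows, because it sets no seriousness condition.

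Step 2. The fourth row can occur under the protocol's own definitions. Section 11.1.3 requires a serious deterioration in health together with one of the listed consequences, such as hospitalization, lasting impairment, or an intervention to prevent it. Whether a case qualifies is a judgment. The note to that section says that the sponsor treats all cancers as serious and, with one exception, abortion. It does not name skin necrosis.

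Step 3. No other section supplies the missing notice. Section 10.4 has no notification clause with a time limit. The 24-hour duty in 11.3 is for AESIs only. Section 11.4, including the sponsor's assessment of whether an event was unanticipated, starts from serious events.

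Step 4. The consequence differs by stage of the 10.4 procedure:
- *Initial suspension at the site.* It follows from the event itself and does not wait for the sponsor, although the text does not say who imposes it.
- *Confirmation and root-cause analysis.* The sponsor carries out the root-cause analysis and, once the event is confirmed, suspends further enrollment as well as treatments at the site. It has to know of the event.
- *Halt at all sites.* It depends on the outcome of the previous stage, so it also waits on the sponsor's knowledge.

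The fourth row is thus a suspension trigger whose sponsor-dependent stages have no timed start.

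**The case against.** Several points weigh against a strong reading, and most of them stand.

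- **The affected site should already have stopped.** Section 10.4 acts when the event occurs, and 10.2 makes the PI responsible for compliance at the site. A reader might infer that injections carry on there until the sponsor learns of the event. The text does not support that for an investigator who follows 10.4.
- **The sponsor is not shut out.** The opening of 10.4 has the sponsor, PI, monitor and others discuss conditions of this kind. Section 10.2 promises frequent contact with the site as well as regular visits, and 12.6 provides for remote and on-site monitoring. The eCRF entry is due as soon as the site is aware. What is missing is active notice and a deadline, not recording.
- **The subset is small.** Necrosis that amounts to a serious deterioration and needs intervention to prevent lasting damage is an SAE, and that criterion does not require the final outcome to be known.
- **The SAP consequence is slight.** SAP 5.6.3 lists all TEAEs and tabulates them by system organ class, preferred term and severity, so skin necrosis would appear. The separate AESI summary is produced only if at least 5 participants have such an event.
- **Stopping and expedited reporting serve different purposes.** This is true, and the sections do not contradict each other outright. But the later stages of 10.4 rely on the sponsor knowing, and the protocol chose not to rely on the seriousness judgment for vision events. No reason is given for relying on it for the other triggers.

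A reader might also multiply a study-wide weekly injection rate by an assumed reporting lag and call the product avoidable exposure. The documents do not support that. They state no lag, and under 10.4 sponsor awareness does not stop all sites at once: an all-site halt is conditional and comes after confirmation. Some injections elsewhere would take place even with 24-hour notice.

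**Conclusion.** The mismatch is in the text, and the point holds in a limited form. Embolic skin necrosis judged non-serious triggers the suspension rule in Protocol 10.4, yet the sponsor is assured of no active or timed notice of it. The effect is a possible delay to the sponsor's confirmation, root-cause and all-site decisions. It is not a failure of the suspension at the affected site.

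The size cannot be given as a number of subjects, because the documents state neither how often such a case would arise nor how long monitor review would take. The conclusion assumes that an investigator could reasonably judge some embolic skin necrosis non-serious under 11.1.3, and that the timelines in 11.2 are applied as written. It does not touch the effectiveness analyses. It is a narrow gap in safety communication, worth closing because closing it is cheap.

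**What to change.** Reconcile Protocol 11.1.2, 11.2 and 11.3 with 10.4 so that every event that triggers the suspension rule is notified to the sponsor by the existing 24-hour fax or e-mail route, whatever its seriousness. One way is to add the 10.4 trigger events to the AESI definition; another is a separate line for them in the 11.2 table with a matching sentence in 11.3. The first also brings them under the 10-working-day FDA notice in 11.3, so the sponsor should choose knowingly. Either way, notice should not wait for the event to be confirmed as embolic, since 10.4 places confirmation after the initial suspension. If the AESI definition changes, match SAP 5.6.3 for consistency.

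The suspension rule and the care of subjects stay as they are.

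The cost is a short protocol amendment, a SAP sentence if needed, a notice to sites, and a few more expedited reports of events that may prove not to be embolic.

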#### 11.1.3 Serious Adverse Event

An SAE is defined in accordance with ISO 14155 as an AE that:

- a) led to death,
- b) led to serious deterioration in the health of the subject, that either resulted in
  - 1. A life-threatening illness or injury, or
  - 2. a permanent impairment of a body structure or a body function, or
  - 3. in-patient or prolonged hospitalization, or
  - 4. medical or surgical intervention to prevent life-threatening illness or injury or permanent impairment to a body structure or a body function,
- c) led to fetal distress, fetal death or a congenital abnormality or birth defect

NOTE: Planned hospitalization for a pre-existing condition, or a procedure required by the protocol, without serious deterioration in health, is not considered an SAE. Allergan considers all cancers as SAEs. Abortion is also considered an SAE except for elective abortion of a normal fetus.

See Section 11.4 for procedures for reporting an SAE/serious adverse device effect (SADE).

